### Study Design and Methods

**Design:** This is a single blinded randomized cross-over study. The participants will be randomly assigned the order of the paradigms viewed in the R-VR or as videos on the computer. The randomization will be through REDCap, as programmed by the study statisticians. The R-VR with the pre-programmed paradigms and corresponding non-VR videos will be labelled A through D. The coordinators will be informed via REDCap about which the experience to provide the participants for each of the study visits: A-D for Visits 1-4.

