## **Video Experience Procedure**

Participants will be scheduled for a 30-min office visit. After a verbal description of the study process and completion of IRB consent form, participants will complete the demographic and other baseline questionnaires.

The coordinator will instruct the participant on certain procedures dependent on the study participant's randomization and visit:

**R-VR Experience:** Study participant will be asked to complete a set of questionnaires, following completion they will be seated in a swivel chair in the center of the research room, given basic instruction on the VR headgear [*Oculus Quest*], and then offered the opportunity to experience the intervention event. The approximately 10 minute VR event involves one of two scenes (randomly selected by REDCap): Scene 1 is designed for relaxation in nature with natural scenery such as trees, streams and deer, or Scene 2 designed to help the participant focus with natural scenery such as glowing embers and fireflies. After a VR experience, the headgear will be removed and the participants will be asked to complete a second round of questionnaires.

**Computer Video Experience:** Study participant will be asked to complete a set of questionnaires, following by being seated at a computer and asked to watch a video with one of two scenes: (Scene 1) natural scenery such as trees, streams and deer; (Scene 2) natural scenery such as glowing embers and fireflies. After this viewing they will be asked to complete a set of surveys.

All will be remunerated up to \$40 at the end of their study participation. This amount will be prorated based on the number of visits completed

This process will provide a within-participant control, allowing us to investigate whether the VR experience is safe and results in significantly more change than the Video experience.

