## **Participant Information**

**Target accrual:** 24 to be randomized (36 to be consented and screened).

**Participant population:** 24 adults

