### Data Analysis

**Power Statement:** The sample size for this pilot investigation (N=24) was established after considering both the statistical implications and the amount of project effort and resources required to recruit and study this unique participant population.

**Data Analysis Plan:** Data related to participant recruitment will be summarized, including the frequency of calls and the reasons for failing screening criteria. In all cases, data will be summarized using mean  $\pm$  SD for continuous variables and frequency percentages for nominal variables. Details will be documented and summarized for any participants who experience adverse events or are unable to complete the 10-minute VR experience for any reason. The percentage of participants who undergo the initial VR experience (V2) but discontinue study participation without returning for the 2nd VR experience (V3) will be summarized and compared between scenes using Fisher's exact test. Anxiety, stress, cognition will be assessed immediately before/after and 24 hours following each VR experience. Within and between group comparisons will be performed using appropriate repeated measures analyses (e.g. paired t-test, repeated measures ANOVA) taking into account the two group repeated measures cross-over study design. In all cases, findings will be summarized using point estimates and corresponding 95% confidence intervals.

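### No handling of missed sessions is stated and only complete-set methods are named as examples, so people who leave after a bad VR session may drop out of the VR-versus-video estimate

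*Combined protocol and SAP*

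**What the plan says.** Each participant is due four sessions, two in VR and two as computer video, one at each of Visits 1 to 4. Under Study Design and Methods, "The R-VR with the pre-programmed paradigms and corresponding non-VR videos will be labelled A through D", and "The participants will be randomly assigned the order of the paradigms viewed in the R-VR or as videos on the computer". Video Experience Procedure presents VR versus video as a within-participant comparison.

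For the outcomes, Data Analysis states: "Within and between group comparisons will be performed using appropriate repeated measures analyses (e.g. paired t-test, repeated measures ANOVA", with the qualifier "taking into account the two group repeated measures cross-over study design". No model, period term, analysis set, missing-session rule or sensitivity analysis follows.

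The same section expects losses. Anyone unable to finish a VR session is to be documented. The plan also counts people who have the initial VR experience "but discontinue study participation without returning for the 2" (the quotation breaks at a superscript; the sentence goes on to the second VR experience). Video Experience Procedure prorates payment by visits completed.

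On timing of the post-session measures, Video Experience Procedure says: "After a VR experience, the headgear will be removed and the participants will be asked to complete a second round of questionnaires".

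On size, Participant Information gives "24 to be randomized (36 to be consented and screened". Data Analysis says "The sample size for this pilot investigation (N=24) was established after considering both the statistical implications", without an effect size, SD, power or withdrawal allowance.

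**The concern.** Both named methods, as usually run, need complete data of some kind: all four sessions for the ANOVA, both formats for a paired VR-versus-video test. Take a participant who has VR at Visit 1, feels worse, completes the post-session questionnaires and does not return. That person has a full pre/post VR record, yet neither method uses it in the VR-versus-video contrast.

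If leaving is related to a poor response to VR, those who remain make VR look better than it is. The effect on anxiety is among the primary aims, and the opening section says the pilot will inform whether a larger efficacy study is developed. With 24 participants, a few selective losses can matter. Because the handling is not stated, it could also be settled after it is known who left.

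A smaller point concerns sessions stopped early. The questionnaire instruction does not say what happens then, so a post-session score could be lost.

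**Working it through.** The documents give no dropout rate, SD or share of poor responders, so N=24 cannot be reproduced and every rate below is an assumption.

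**1. Who is kept, by order.** Take all 24 orders of two VR and two video sessions as equally likely.
- Leaving after the first VR session: none has all four sessions, so listwise ANOVA drops all of them. Half already have a video session, so a paired test on available VR and video means keeps half. One third have the video of the same scene, so a scene-matched pair keeps one third.
- Leaving after the second VR session: half have all four sessions and 83% have at least one video.

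**2. Precision, if a fraction w of those remaining leaves after each session.**
- Completers = 24 × (1−w)³: 24 × 0.95³ = 20.6 and 24 × 0.90³ = 17.5.
- Sessions collected = 24 × [1 + (1−w) + (1−w)² + (1−w)³]: 24 × 3.710 = 89.0 and 24 × 3.439 = 82.5.
- Sessions used by complete cases = 4 × completers: 82.3 and 70.0, a loss of 8% and 15%.
- For scale, the paired difference detectable with 80% power (two-sided 5%, assumed) is 0.60 SD of the differences at n=24, 0.66 at n=20 and 0.70 at n=18.

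**3. Bias, illustrative.** Assume that 15% respond poorly to VR (anxiety change +5; the others −5), that video gives −2 for all, and that 80% of poor responders leave after each VR session. The VR-minus-video difference is then +7 in poor responders and −3 in the others. If poor responders make up a share p of those analysed, the estimate is −3 + 10p.
- True value: p = 0.15, giving −1.5.
- Complete cases: the last session is VR in half the orders (one chance to leave before it) and video in the other half (two chances). A poor responder completes with probability ½ × 0.2 + ½ × 0.04 = 0.12. Then p = 0.018/(0.018 + 0.85) = 0.021, giving −2.8 with 24 × 0.868 = 20.8 people.
- Paired means of available sessions: a poor responder has both formats with probability ½ + ⅓ × 0.2 + ⅙ × 0.04 = 0.573. Then p = 0.086/(0.086 + 0.85) = 0.092, giving −2.1 with 24 × 0.936 = 22.5 people.
- Mixed model on all attended sessions: simulations with several assumed SDs gave −2.0 to −2.3. The same kind of simulation gave −2.7 to −2.9 for complete cases and −2.0 to −2.2 for paired available means.

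The size depends heavily on the inputs (same formulas):

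| Poor responders | Leave after each VR session | True | Complete cases | Paired available means |
|---|---|---|---|---|
| 15% | 80% | −1.5 | −2.8 | −2.1 |
| 15% | 40% | −1.5 | −2.2 | −1.8 |
| 5% | 80% | −2.5 | −2.9 | −2.7 |

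Row 2: completion ½ × 0.6 + ½ × 0.36 = 0.48, p = 0.072/0.922 = 0.078; both formats ½ + ⅓ × 0.6 + ⅙ × 0.36 = 0.76, p = 0.114/0.964 = 0.118. Row 3: p = 0.006/0.956 = 0.006 and 0.0287/0.9787 = 0.029.

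**4. A different leaving mechanism.** In a second simulation, people left after a VR session whose observed change was worse than a threshold (between-person SD 0.5, residual SD 0.7, person-by-VR SD 0 or 0.5). Complete cases overstated the VR benefit by 0.01 to 0.18 score units, the largest with about 5 of 24 leaving. Paired available means overstated it by 0.00 to 0.05. A mixed model was within about 0.01. This is a best case for the model: leaving depended only on observed scores, and the covariance was treated as known.

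**The case against.** The strongest reply is that the plan does not commit to dropping anyone. Its methods follow the words *appropriate* and *e.g.*, it must respect the cross-over design, and a mixed model would fit the same sentence. That stands. A reader might infer that the plan prescribes a complete-case analysis, but no section says so. The gap is that no handling of missed sessions is stated and the only examples given are methods that usually require complete pairs or sets.

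A reader might also infer that everyone who leaves after a bad VR session vanishes. The documents do not support that either. Because order is random, a paired test keeps one third to one half of those who leave after their first VR session, and half of those who leave after their second have complete data. Within-session pre/post comparisons keep all who gave both scores. Adverse events, unfinished VR sessions and discontinuation are summarised separately. However, the discontinuation comparison is between scenes, not VR against video. It also labels the two VR experiences V2 and V3, while Study Design and Methods randomises order over Visits 1 to 4. Those passages need to be reconciled before the summary can be relied on to catch these withdrawals.

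Third, paired means of available sessions do as well as the mixed model in the scenario above. That also stands: the bias reduction is relative to complete-case ANOVA only.

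Fourth, the inputs have no anchor, and the exclusion criteria remove people who cannot tolerate VR, which may make poor responses rarer. That is fair, and it is why the size is given only as illustration.

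Finally, a reader might infer that early stoppers get no second questionnaire. The text does not limit that round to completed sessions. It leaves the case open.

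**Conclusion.** The point holds as a gap in the analysis plan worth closing. Participants who leave after a bad VR session may be excluded from the VR-versus-video estimate, and any resulting bias would favour VR. Its size cannot be determined from the documents. In the main illustration complete cases overstate the benefit by about 1.3 points (−2.8 against −1.5). A mixed model or paired available means overstate it by about 0.5 to 0.8 (−2.0 to −2.3 against −1.5). With milder assumptions the complete-case excess falls to 0.7 (−2.2 against −1.5) or 0.4 (−2.9 against −2.5), and it is nil if leaving is unrelated to response. These figures rest on assumed response and leaving rates and on equally likely orders. Safety, acceptability and adherence are also primary aims with their own measures, so poor reactions are not hidden from the decision on a larger study. What is at risk is the efficacy contrast.

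**What to change.** In Data Analysis, name one linear mixed model: random participant effect; fixed effects for format, scene, period and pre-session score. State that it includes every attended session from every randomised participant, including those who later withdraw.

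In Video Experience Procedure, state that the second questionnaire round is requested whenever a session ends, completed or stopped early, and that the session is analysed under its assigned experience.

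The cost is a few sentences of analysis wording and one line of coordinator procedure. The downside is that the model assumes data are missing at random given the observed sessions, so it reduces the bias of complete-case ANOVA without removing it. A sensitivity analysis for informative withdrawal would be a useful addition, especially where a stopped session leaves no post-session score. Compared with a paired test on available sessions, the model keeps people seen in only one format and adjusts for period and pre-session score. It should not be presented as a clear further cut in bias.

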## Visit Flow and Timeline

Visit Number	Day 0	Day 1		Day 4		Day 7		Day 10	
	V0 	V1a 	V1b	V2a	V2b	V3a	V3b	V4a	V4b
		Consent + 0 day to +7 days from	Immediately following VR/Video	Prior to VR/Video	Immediately following VR/Video	Prior to VR/Video	Immediately following VR/Video	Prior to VR/Video	Immediately following VR/Video
Informed Consent	X 								
Inclusion/Exclusion	X								
Demographics Form	X								
Medical History	X								
Adverse Events	X	X		X		X		X	
Concomitant Medications	X	X		X		X		X	
R-VR Intervention			X		X		X		X
Brief Resilience		X		X		X		X	
Evaluate Response to the VR experience (HUMAN)		X	X	X	X	X	X	X	X
Emotional distress		X	X	X	X	X	X	X	X
Cognitive Function		X	X	X	X	X	X	X	X
Self-efficacy		X		X		X		X	
Anxiety		X	X	X	X	X	X	X	X
Satisfaction Survey									X

Consent can be completed digitally in person or through remote consenting

Visit 0 and Visit 1 can occur on same day or on separate occasions at the participant's convenience.

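### The VR-versus-video question is framed as change, with no adjustment for each session's own pre-session score; adjusting for it is expected to give a narrower interval from the same 24 people.

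*Combined protocol and SAP*

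**What the plan says.** The Study Design and Methods section states: "This is a single blinded randomized cross-over study". Each participant has four sessions (two scenes, each in VR and as a computer video), assigned as "A-D for Visits 1-4". The Video Experience Procedure section explains that participants act as their own controls, to learn whether VR is safe and "results in significantly more change than the Video experience".

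The Visit Flow and Timeline table marks Anxiety (the STAI), Emotional distress and Cognitive Function at V1a to V4a and again at V1b to V4b. The columns V2a to V4a are headed "Prior to VR/Video", and V1a plays the same part for the first session.

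The Data Analysis section says that within- and between-group comparisons will be made "using appropriate repeated measures analyses (e.g. paired t-test, repeated measures ANOVA"), allowing for the cross-over design, and that "findings will be summarized using point estimates and corresponding 95% confidence intervals". It does not say whether the outcome is a change or a post-session score, and it names no covariate. No adjustment for the pre-session score appears elsewhere.

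Of the listed primary aims, the third concerns the impact of R-VR on anxiety and inattention. The fourth compares the two R-VR paradigms on anxiety and relates this to baseline self-efficacy. VR minus video is not a listed aim; it comes from the Video Experience Procedure section.

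**The concern.** If the question is about change, the two named methods lead to the same analysis. A paired t-test on pre-to-post change and the condition-by-time test of an ANOVA with pre and post as two levels both subtract the whole pre-session score, which fixes its slope at 1. State anxiety varies from day to day. When a person arrives unusually tense, part of that deviation would be expected to fade by the post-session form whatever was shown. Subtracting all of it adds noise to the VR-minus-video contrast and carries chance differences between VR days and video days into the estimate.

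The cost is precision, not validity. With 24 people, and with results promised as estimates and intervals that will inform whether a larger study is developed, interval width matters. The covariate that would recover some of that precision is already on the schedule.

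**Working it through.** **The plan's own figure.** The target is "24 to be randomized (36 to be consented and screened"). The basis given is: "The sample size for this pilot investigation (N=24) was established after considering both the statistical implications and the amount of project effort". No effect size, SD, correlation, alpha or power is stated, so N=24 cannot be reproduced. For orientation, taking two-sided 5% from the planned 95% intervals, 24 pairs give 80% power for (1.960 + 0.842)/√24 = 0.57 SDs of the paired difference (0.60 with the t distribution).

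**Inputs.** From the documents: 24 people, four sessions each, and pre and post scores at every session. Assumed: r, the within-person correlation of pre and post scores across sessions (0.3 to 0.7 as the main range), and k, the ratio of post SD to pre SD (1 as the main case; 0.8 and 1.25 as checks). The within-person r is the right input, because differences between people cancel in a cross-over contrast.

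**Formula.** With s the within-person pre-session SD, the residual variances are:

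- change score: s²(1 + k² − 2rk)
- adjusted for the pre-score: s²k²(1 − r²)

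The large-sample interval-width ratio, adjusted to change, is √[k²(1 − r²)/(1 + k² − 2rk)]. With k = 1 the variance ratio is (1 − r²)/[2(1 − r)] = (1 + r)/2.

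**Finite-sample check.** Simulations used 24 people, complete normal data and balanced orders. The four-session model has 24 × 4 = 96 observations. Intercept 1, persons 23, visits 3, scene 1, format-by-scene 1 and format 1 use 30 degrees of freedom, leaving 66, or 65 with the pre-score. The paired contrast reduces each person to one VR-minus-video difference (23 against 22 degrees of freedom).

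Results with k = 1:

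| r | Variance ratio | Large-sample width ratio | People needed with change scores | Simulated width ratio, four-session | Simulated width ratio, paired contrast |
|---|---|---|---|---|---|
| 0.3 | 0.65 | 0.81 | 24/0.65 = 36.9 | 0.81 | 0.83 |
| 0.5 | 0.75 | 0.87 | 24/0.75 = 32.0 | 0.87 | 0.89 |
| 0.7 | 0.85 | 0.92 | 24/0.85 = 28.2 | 0.93 | 0.95 |
| 0.9 | 0.95 | 0.97 | 24/0.95 = 25.3 | 0.98 | 1.00 |

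In the four-session model the interval is 19%, 13% and 7% narrower at r = 0.3, 0.5 and 0.7. Coverage of the paired contrast was about 95% for both methods, and type I error in the four-session model was near 5% for both.

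**Sensitivity to the SD ratio.** The within-person slope of post on pre is rk.

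- k = 1.25: four-session width ratios are 0.89, 0.95 and 1.00 at r = 0.3, 0.5 and 0.7. At r = 0.8 the slope is 0.8 × 1.25 = 1, and the paired-contrast interval is about 2.5% wider with adjustment.
- k = 0.8: paired-contrast ratios are 0.73, 0.78 and 0.81 at r = 0.3, 0.5 and 0.7.

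**How often a single trial benefits (k = 1).** In the four-session model the adjusted interval was the narrower one in nearly all runs at r = 0.3 and 0.5, in 96% at 0.7 and in 67% at 0.9. For the paired contrast the figures are 95%, 86%, 70% and 41%.

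**If post-session scores alone were intended.** The slope is then fixed at 0. Adjusted-to-post width ratios for the paired contrast are 1.02, 0.98, 0.89 and 0.73 at r = 0.1, 0.3, 0.5 and 0.7.

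**The case against.** A reader might infer that the plan prescribes raw change scores. It does not. The methods in the Data Analysis section are examples, and the framing as change comes from one sentence in a procedures section. That sentence is itself compatible with adjustment: regressing change on the pre-score gives the same format coefficient as regressing the post-score on it. What stands is that no adjustment is specified and that the natural reading of the named methods, applied to change, omits it.

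A reader might also infer that adjustment is certain to narrow the interval. The documents give neither r nor k, and the sensitivity results show cases with no gain or a slight loss. Nor can the change analysis be called invalid, since its coverage and type I error hold.

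Two further objections stand and shape the remedy. First, replacing the paired t-test outright would lose the direct pre/post estimate for aim 3, and a model with only additive format and scene terms would not estimate the contrast between the two R-VR scenes for aim 4. Second, pre-session scores at visits 2 to 4 follow earlier sessions. A carried-over shift present both before and after a session cancels in a change score, while adjustment leaves (1 − slope) of it. A shift present only before the session biases change in full and the adjusted score by the slope fraction. Neither method is immune, so it is useful to report both.

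**Conclusion.** The point holds as one of efficiency and specification. For VR minus video, the plan frames the question as change and names methods without baseline adjustment, although a pre-score exists for every session. With equal pre and post SDs and a within-person correlation of 0.3 to 0.7, both assumed, adjustment is expected to narrow the 95% interval by about 19% to 7% in the four-session model. In large samples that matches enrolling about 37 to 28 people for a change-score analysis instead of 24. The gain fades as the within-person slope approaches 1, and the largest loss in the settings examined was about 2.5%. The figures also assume complete, roughly normal data, balanced orders and no carry-over into later pre-session scores. No power gain is claimed, because the documents give no effect size or SD.

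**What to change.** In the Data Analysis section:

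- Keep the paired within-session pre/post summaries for aim 3.
- For between-condition comparisons of the STAI, the adapted distress form and Cognitive Function, specify a linear mixed model of the post-session score. Include a random participant effect and fixed effects for format, scene, format-by-scene and visit. Enter the pre-session score as two terms, the participant's mean and that session's deviation from it, so that the format contrast stays within person.
- Report VR minus video (averaged over scenes) and R-VR scene 1 minus R-VR scene 2, each with a 95% interval.
- Report the change-score analysis as a sensitivity analysis, and say that the adjusted model assumes no carry-over into later pre-session scores.

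The cost is wording and a few model degrees of freedom. No new visit, form or participant is needed.

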#### Acceptability and Adherence to Intervention:

- Acceptability will be measured through the patient satisfaction survey at the end of the study.
- Adherence to the R-VR will be assessed by collecting attendance for study visits 1-4.

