#### Resources

REDCap will be utilized for data collection using created online forms. Clinician investigators will provide medical oversight. Tools needed for this intervention include one R-VR for each paradigm for a total of 2 R-VRs and a computer for the non VR experiences.

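### The analysis plan does not match the four-period VR/video crossover: its V2/V3 discontinuation labels do not fit a randomised order, and the VR-minus-video contrast is not named

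*Combined protocol and SAP*

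**What the plan says.** **Design.** Under Study Design and Methods, "The participants will be randomly assigned the order of the paradigms viewed in the R-VR or as videos on the computer". The same paragraph adds that "The R-VR with the pre-programmed paradigms and corresponding non-VR videos will be labelled A through D", with A-D assigned to Visits 1-4 through REDCap. Resources lists "one R-VR for each paradigm for a total of 2 R-VRs and a computer for the non VR experiences". There are therefore four conditions (two scenes, each by VR and by video) over four visits. In the Visit Flow and Timeline table every post-session column is headed "Immediately following VR/Video", and no visit is fixed as VR or as video. Anxiety, emotional distress and cognitive function are collected before and after every session.

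**Question.** Video Experience Procedure says that the within-participant control is there for "allowing us to investigate whether the VR experience is safe and results in significantly more change than the Video experience".

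**Analysis.** The Data Analysis section summarises the percentage of participants who "undergo the initial VR experience (V2) but discontinue study participation without returning" for the second VR experience, which it labels V3, and compares this between scenes with Fisher's exact test. It ties outcome assessment to each VR experience and plans within- and between-group comparisons by repeated measures methods, "e.g. paired t-test, repeated measures ANOVA) taking into account the two group repeated measures cross-over study design". The word video does not appear in that section, and the two groups are not defined.

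**The concern.** There are two mismatches of unequal weight.

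1. The discontinuation summary attaches fixed visit numbers to the first and second VR sessions, but the order of VR and video is randomised. For most orders V2 is not the first VR session, or V3 is not the second. A programmer who follows the labels would count some people wrongly and miss others. Adherence is one of the primary aims, and the pilot results are to inform the decision on a larger efficacy study, although the protocol does not say which aim decides.

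2. The design provides a video comparator, but the analysis section does not name the contrast that uses it. The two groups could be VR and video, the two scenes of Aim 4, or two sequence groups. Aim 3 names no comparator. A pre-post drop after VR might then be read as an effect of VR, although a nature video might produce the same drop.

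**Working it through.** **Inputs.** Four conditions and four visits, one condition per visit (Study Design and Methods); the V2 and V3 labels (Data Analysis); 24 participants to be randomised (Participant Information). The documents do not say which orders are used, with what probabilities, or how much drop-out is expected. Equal order probabilities and the drop-out patterns below are assumptions. The plan gives no figure of its own on this point to reproduce.

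**Step 1: where the VR sessions fall.** There are 4! = 24 orders. The two VR sessions can occupy 6 pairs of visits, each arising from 2 × 2 = 4 orders (order of the VR scenes × order of the video scenes).

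| VR at visits | Orders | VR sessions done after V1 | after V2 | after V3 |
|---|---|---|---|---|
| 1, 2 | 4 | 1 | 2 | 2 |
| 1, 3 | 4 | 1 | 1 | 2 |
| 1, 4 | 4 | 1 | 1 | 1 |
| 2, 3 | 4 | 0 | 1 | 2 |
| 2, 4 | 4 | 0 | 1 | 1 |
| 3, 4 | 4 | 0 | 0 | 1 |

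V2 is a VR session in 12 orders and the first VR session in 8. V2 and V3 are the first and second VR sessions in 4 of 24. Any fixed pair of visits would fit 4 of 24, so shifting the visit numbering does not rescue the labels.

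**Step 2: who is counted wrongly among those leaving after V2.** The target is people with exactly one VR session done.
- After V2, 16 orders give one VR session, 4 give none and 4 give both.
- If everyone leaving after V2 is counted: (4 + 4)/24 = 8/24 = 33% wrong.
- If prior VR exposure is also required, the 4 orders with none drop out: 4/(16 + 4) = 4/20 = 20% wrong.

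**Step 3: who is missed.** Exactly one VR session has been done in 12, 16 and 12 of 24 orders when leaving after V1, V2 and V3. The labels can find only the V2 leavers.
- Drop-out equal after V1, V2, V3: missed = (12 + 12)/(12 + 16 + 12) = 24/40 = 60%.
- Split 25/50/25: true cases 0.125 + 0.333 + 0.125 = 0.583; missed 0.250/0.583 = 43%.
- Split 50/30/20: true cases 0.25 + 0.20 + 0.10 = 0.55; missed 0.35/0.55 = 64%.

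**Step 4: other randomisation schemes that the protocol does not exclude** (missed share at equal drop-out).

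| Scheme | Counted wrongly | Missed |
|---|---|---|
| All 24 orders equally likely | 33% or 20% | 60% |
| VR and video alternate | 0% | 50% |
| Blocked by modality (8 orders, labels fit none) | 100% | 100% |
| Fixed video-VR-VR-video, scenes randomised | 0% | 0% |

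**Step 5: in people.** With 3 drop-outs among 24 (assumed), one after each of V1, V2 and V3, the rule counts 1 person, expected 8/24 = 0.33 wrongly, and misses 12/24 + 12/24 = 1.

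**Step 6: the VR-versus-video contrast.** No arithmetic is needed. Video Experience Procedure gives the comparator (video), the measure (change) and the direction (more with VR). The Data Analysis section supplies a compatible class of methods but no contrast, and its sentence on outcome timing mentions VR only.

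**The case against.** **On discontinuation.** The operative words refer to exposure: someone must have had the initial VR experience and not return for the second. V2 and V3 stand in parentheses and may be leftover labels. If the words govern, nobody is misclassified. This stands as a limit on size, and it is why 4 of 20 is given beside 8 of 24. A reader might infer that a third of the counted drop-outs would be wrong. The documents do not support that as a finding: it requires ignoring the exposure wording, it assumes equally likely orders, and the share runs from 0% to 100% over schemes that the protocol leaves open. The objection does not make the labels right. They fit everyone only under a fixed video-VR-VR-video order, which no section states.

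**On the contrast.** This is one combined document. Video Experience Procedure already states the VR-versus-video question, and the between-group crossover wording in Data Analysis permits that comparison. VR wording is used loosely elsewhere: the timeline marks the R-VR intervention at all four visits, and "Adherence to the R-VR will be assessed by collecting attendance for study visits 1-4". A reader might infer that the video data would be left out, or that an uncontrolled VR change is planned as the efficacy result. Neither follows, since the omission of video may be shorthand. What stands is that the contrast is unnamed and the two groups undefined, so the choice remains open until after the data are seen.

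**On method.** The existing wording already allows any suitable repeated measures model, so a particular model or adjustment for the pre-session score would be a preference and is not part of this point.

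**Conclusion.** The Data Analysis section should be reconciled with the design sections.

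The V2/V3 labels are wrong as written. If all 24 orders are equally likely, they identify the first and second VR sessions in 4 of 24. The consequence is small in absolute terms, about one person if drop-out is low, and it disappears if the exposure wording is followed instead of the labels. The percentages rest on assumed order probabilities and drop-out timing and should not be quoted without their ranges.

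The missing mention of video and the undefined two-group label are a smaller point of clarity. The comparison is intended and permitted, but the section does not name it. No stated figure in the plan is shown to be wrong.

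**What to change.** **Discontinuation.** Delete the V2 and V3 labels. Define discontinuation as completing one's own first VR session and leaving the study without one's own second, whatever the visit numbers. Compare by the scene of the first VR session. Every participant sees both scenes in VR, so this grouping gives Fisher's exact test two separate groups.

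**Contrast.** Describe the design as a two-by-two (modality × scene), four-period crossover, and refer to each VR/video session. Name two within-participant contrasts of pre-post change, each with a 95% confidence interval:
- VR minus video, averaged over scenes, for the question under Video Experience Procedure;
- VR scene 1 minus VR scene 2, for Aim 4.

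State that pre-post change within VR will not be read as an effect of VR over video. The investigators should confirm the main contrast for Aim 3. The model and any adjustment for the pre-session score are for the study statisticians to choose.

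**Cost.** A few sentences and a little analysis work. No new data are needed: the pre and post scores are collected at every session, the order is assigned through REDCap, and attendance is collected for Visits 1-4.
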